Giant cellular arteritis (GCA) (or Horton's disease) is a vasculitis characterized histologically by an inflammation, most often transmural, made up of lympho-mono-macrophagic cells, sometimes of giant cells that can narrow the lumen of the artery and lead to thrombosis. It involves medium and large caliber vessels (preferential involvement of the branches of the external carotid, including the superficial temporal artery), but all the large arterial trunks may be involved, including the aorta (1, 2). GCA is the most common systemic vasculitis in Western countries. Its geographical distribution follows a frequency gradient which decreases from the north to the south of Europe. In France, its prevalence is around 1 per 1000 among the over 50s.

Indeed, GCA generally affects people over the age of 50, with a peak frequency between 70 and 80 years. A recent English work estimated the incidence of GCA at 1.2 per 10,000 patient-years, but 7.4/10,000 for women aged 70-79 years (3).

The diagnostic delay is sometimes several months (4, 5) while there is a visual risk with the possibility of irreversible blindness (10-15% of patients) and an increased risk of cardiovascular accident (6-8) .

Indeed, the diagnosis of GCA is a real challenge for the general practitioner or specialist. Since 1970, it has been based on a combination of clinical, biological and histological signs grouped together in part in the classification criteria of the American College of Rheumatology (9, 10).

Thus, the temporal artery biopsy (TAB), most often unilateral, was considered until recently as the reference method. Nevertheless, the TAB poses many problems:

- technical: invasive nature of the surgical procedure, sampling failure, local complications (abscess, hematoma, pain, nerve damage), management of anticoagulants, patient refusal
- logistical orders: accessibility of the operating room, extension of the hospitalization period

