The end of the research corresponds to the end of the participation of the last person who agrees to the research.

In the event of premature termination of the study, the information will be transmitted by the person in charge within 15 days to the CPP.

4.6- Identification of all the data to be collected directly in the observation notebooks, which will be considered as source data

A blank paper copy of the e-CRF can be printed from the e-CRF. The supervisor will therefore have the possibility of directly reporting the biological, clinical and radiological data of the patients included in it to facilitate data entry. The supervisor must date and sign this copy at the end of data collection.

This document will be an integral part of the patient's medical file and will be kept there permanently. The data recorded in the e-CRF and coming from the source documents must be consistent with each other; otherwise, the differences must be justified and documented.

The rereading results of the TAB slides and Doppler echo images will be recorded in the e-CRF.

5. Selection and exclusion of persons from research

5.1- Inclusion criteria

- Patient cared for in one of the participating centers
- ≥ 50 years
- CRP higher than laboratory normal
- GCA suspects defined by:
 - o Patients suspected of GCA according to the expert clinician and/or
 - o Aortitis or arteritis of one or more arteries originating from the aorta on imaging (angio-CT, angio-MRI or PET-CT18FDG)
- Benefiting from Social Security or benefiting from it through a third party
- Having given their consent to participate by understanding and accepting the constraints of the study

5.2- Criteria for non-inclusion

- Patient who received a dose of corticosteroid therapy ≥ 20 mg prednisone equivalent for > 7 days in the month prior to inclusion
- Patient having undergone a temporal artery biopsy before carrying out an echo-doppler.
- Patient with a personal history of GCA
- Patient in the terminal palliative phase or suffering from a pathology or comorbidities such that the vital prognosis is committed at less than one year
- Patient with severe cognitive impairment
- Patient who cannot be monitored by the supervisor for the duration of the study (e.g. vacationers)
- Refusal to participate in the study
- Not benefiting from a Social Security scheme or not benefiting from it through a third party

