Knowing that the diagnosis of GCA is difficult, the majority of patients likely to be carriers of Horton are referred to clinicians. However, to account for patients not cared for by monitors participating in the study and patients refusing to participate, the goal is to include 45-50% of suspected Horton cases.

Center	Recruitment objective (Nb patients/month)	Duration of inclusion (months)	Forecast over the entire duration of the study
La Rochelle	2	24	48
Rochefort	1.5	24	36
Poitiers	2	24	48
Niort	1.5	24	36
Angouleme	1	24	24
Nantes	2	12	24

Table 3: goal of inclusion

7.3- Expected degree of statistical significance

The statistical tests will be carried out at the bilateral alpha risk of 5%.

7.4- Statistical criteria for stopping research

An interim analysis at 1 year of the start of inclusions will be made. Depending on the results (absence or presence of an alternative diagnosis in the group considered to have GCA on a clinical-biological suspicion + "positive" echo-Doppler) the study will be continued or not.

7.5- Method for taking into account missing, unused or invalid data

In case of premature termination and non-compliance with the protocol, the reasons will be documented. Missing data will be described in terms of numbers and corresponding percentages for each criterion and at each visit. There are no plans to replace patients exiting the study.

Patients suspected of Horton's disease are treated with corticosteroids. The administration of this treatment requires regular dose reviews. Patients are therefore monitored regularly in current practice and few loss of follow-up are expected in the study. On the other hand, cortisone treatment allows a good clinical evolution in patients with gigantocellular arteritis and the response to treatment in the very old subject seems comparable to that of the younger subject. The expected death rate is therefore that of the general population of the same age. Thus, if less than 5% of the patients in the study are lost to follow-up or died, the missing data will be replaced by deductive imputation when possible (e.g. patients with a combination of clinical signs, biological and examinations in favor of a horton and a good evolution under corticosteroids will be classified as suffering from Horton's disease). In the event of a higher rate of missing data, other methods of managing problematic data will be considered.

7.6- Management of modifications made to the analysis plan of the initial strategy

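### Section 7.5 ties the handling of lost or dead patients to an underived 5% trigger over all patients: below it, imputation can lean on the test being validated; above it, no method is fixed

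*Combined protocol and SAP*

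**What the plan says.** Section 7.5 says that missing data will be described by number and percentage for each criterion and visit, and that patients who leave are not replaced. On attrition it says that "few loss of follow-up are expected in the study" and that "The expected death rate is therefore that of the general population of the same age". It gives no figure for either.

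The imputation rule follows: "Thus, if less than 5% of the patients in the study are lost to follow-up or died", then "the missing data will be replaced by deductive imputation when possible". Its printed example is a patient whose clinical signs, laboratory results and examinations point to the disease and who does well on corticosteroids; that patient is classed as a case. Otherwise: "In the event of a higher rate of missing data, other methods of managing problematic data will be considered".

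Related provisions:
- Section 4.1.1: the main criterion is the number of alternative diagnoses within 2 years among CDU-positive patients.
- Section 7.1: the analysis gives the PPV of CDU, and the algorithm is valid only if there is no alternative diagnosis in that group.
- Section 4.2.2.2: CDU-positive patients have no temporal artery biopsy.
- Section 7.6 provides no procedure for changing the analysis plan. Section 7.7 includes eligible and evaluable subjects without defining evaluable.

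**The concern.** The primary result is a zero-or-not-zero count in one subgroup, so the classification of each CDU-positive patient who dies or is lost matters. Section 7.5 leaves that classification open to three problems.

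1. **Direction of the imputation.** For a CDU-positive patient, the examinations in favour of the disease include the positive CDU, and there is no biopsy to set beside it. Imputing a true positive partly from the index test favours the conclusion under test.
2. **Wrong denominator.** The trigger counts all study patients, so it does not limit the share unverified in the group that carries the primary result.
3. **Nothing fixed beyond it.** Past 5%, the method is chosen once the missing cases, and possibly their likely diagnoses, are known.

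At stake is whether a finding of no alternative diagnosis reflects verified patients or the handling of unverified ones.

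**Working it through.** **Inputs from the protocol.** N = 168 and a 70% confirmation rate (7.2); 5% trigger (7.5); 24 months of follow-up (4.4); CDU sensitivity 69% in the sponsor's retrospective series and 96% in a cited study (2.1).

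**Assumptions.** Annual mortality m and 2-year loss l are not printed, so a range is shown.

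**The plan's own figures.** 100/0.70 = 142.9, against 142 stated. The target of 168 corresponds to 100/168 = 59.5% confirmed. The 5% has no calculation to reproduce.

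**Where the trigger falls.** 8/168 = 4.8% and 9/168 = 5.4%, so the rule is lost at the 9th death or loss. Deaths alone reach 5% over 2 years when 1 − (1 − m)² = 0.05, that is m = 1 − √0.95 = 2.53% a year.

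**Chance that the rule is lost.** q = 1 − (1 − m)²(1 − l); P(X ≥ 9) with X ~ Binomial(168, q).

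| m per year | l = 0: q | P(lost) | l = 2%: q | P(lost) |
|---|---|---|---|---|
| 1% | 2.0% | 0.7% | 3.9% | 22% |
| 1.5% | 3.0% | 6.5% | 4.9% | 45% |
| 2% | 4.0% | 22% | 5.9% | 66% |
| 2.5% | 4.9% | 45% | 6.8% | 82% |
| 3% | 5.9% | 67% | 7.8% | 91% |
| 4% | 7.8% | 92% | 9.7% | 98.5% |

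The answer depends almost wholly on inputs that the protocol leaves out.

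**Denominator.** Taking only true positives, the CDU-positive group is about 168 × 0.70 × 0.69 = 81. With 60% confirmed it is 168 × 0.60 × 0.69 = 70; with 96% sensitivity, 168 × 0.70 × 0.96 = 113. Eight missing patients satisfy the trigger. If all were CDU-positive, they would be 8/81 = 9.9% of the group (8/70 = 11.4%; 8/113 = 7.1%). If missingness is unrelated to the CDU result, the expected number is 8 × 81/168 = 3.9, and the chance that all eight are CDU-positive is C(81,8)/C(168,8) = 0.24%.

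**Effect on the primary result with no alternative diagnosis seen.** With n of n confirmed, the exact two-sided 95% lower limit is 0.025^(1/n).

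| Unverified of 81 | Handling | PPV | Lower limit |
|---|---|---|---|
| 8 | all imputed as disease (n = 81) | 100% | 95.5% |
| 8 | verified only (n = 73) | 100% | 95.1% |
| 8 | all counted as alternative diagnoses | 73/81 = 90.1% | – |
| 4 | verified only (n = 77) | 100% | 95.3% |
| 4 | all counted as alternative diagnoses | 77/81 = 95.1% | – |

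Imputation barely moves the interval. What it hides is the gap between 100% and the worst case, which a zero-event validity rule cannot ignore.

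**The case against.** A reader might infer that the rule will usually fail, because section 2.1 describes a disease "with a peak frequency between 70 and 80 years" and mentions raised cardiovascular risk. The documents do not support that:
- They print no mortality and no age distribution. With no losses, the rule still applies with probability 99%, 94% and 78% at 1%, 1.5% and 2% a year.
- Peak disease age is not cohort mortality. Inclusion starts at 50, and section 5.2 excludes severe cognitive impairment, people staying in health or social establishments, and pathology or "comorbidities such that the vital prognosis is committed at less than one year".
- The cardiovascular remark comes in a sentence about diagnostic delay and states no excess death rate, so it does not contradict section 7.5.

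Other fair points:
- Section 7.5 words 5% as a condition and does not forecast it.
- It expects few losses among all suspected patients, and section 4.2.2.2 allows telephone follow-up at M3, M12 and M24 for those with an alternative diagnosis.
- It already requires missing data to be described for each criterion, which would show much of the unverified count.
- It asks for supporting signs and a good clinical course, so the imputation does not rest on CDU alone.
- Eight missing patients all being CDU-positive is a worst case.

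These points remove any claim about how often the trigger is crossed. They do not supply a derivation, a denominator matched to the primary criterion, a method above 5%, or independence of the imputation from the index test. Describing missing data does not say how a missing patient counts.

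**Conclusion.** The concern holds in this form: the trigger is underived and counted over the wrong group, imputation below it favours a high PPV, and nothing is specified above it. None of this needs a mortality assumption. How likely the trigger is to be crossed does need one, and that likelihood is undetermined: from about 1% to 92% for 1% to 4% mortality a year with no losses.

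The numerical effect on the interval is small (95.5% to 95.1% with 8 of 81 unverified). The effect on what can be claimed is larger: a reported 100% would be compatible with a worst case of 90.1%, or 95.1% with 4 unverified. The group size of 81 assumes 70% confirmation, 69% sensitivity and no false positives. This should be changed before the analysis, and wording is enough.

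**What to change.** Delete the 5% trigger in section 7.5 and apply one rule in the CDU-positive group, whatever the missing rate:

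1. **Primary PPV:** patients whose diagnosis is verified at 24 months, plus any with an alternative diagnosis found earlier (counted as such even if they later die or are lost), with an exact binomial 95% interval.
2. **Reported beside it:** the number of CDU-positive patients unverified at 24 months, split by death and loss.
3. **Sensitivity analyses:** deductive imputation as now described, and a bound counting every unverified patient as an alternative diagnosis.
4. **Section 7.7:** define evaluable for the primary criterion to match item 1.

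A cumulative-incidence estimate with death as a competing event is not a good substitute. It would treat deaths without an alternative diagnosis as true positives, and its standard interval collapses when there are no events, the only result that validates the algorithm.

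Cost: SAP wording only, with no extra patients or visits. The downside is a slightly wider interval and a less favourable stated result. Keeping early alternative diagnoses while dropping patients lost without one pulls the estimate slightly down, which is the cautious direction here.

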- Benefiting from enhanced protection, namely persons deprived of their liberty by a judicial or administrative decision, persons staying in a health or social establishment, adults under legal protection, and finally patients in an emergency situation.
- Patient participating in another clinical trial.
- Pregnant or breastfeeding women, women of childbearing age who do not have effective contraception (hormonal/mechanical: oral, injectable, transcutaneous, implantable, intrauterine device, or surgical: tubal ligation, hysterectomy, total oophorectomy)

5.3- Recruitment methods

Patients followed in the internal medicine department of the participating centers and suspected of having giant cell arteritis will be offered to participate in the study.

5.4- Procedure for premature termination of research or exclusion of a person from research and procedure for monitoring the person

The withdrawal of a patient from the study will in no way change his usual care in relation to his illness. In the event of an adverse event, whether serious or not, precise monitoring may be considered depending on the seriousness of the adverse event and the severity. In the context of a withdrawal of non-objection, the data collected will not be used in accordance with the patient's wishes.

6- Safety assessment

6.1- Procedures put in place for the recording and notification of adverse events

The occurrence of an Adverse Effect related to the treatment of the patient during this protocol will give rise to a declaration in the appropriate vigilance system (pharmacovigilance, biovigilance, haemovigilance, materiovigilance, etc.).

6.2- Supervisory Committee

Not planned.

7.- Statistics

7.1- Description of planned statistical methods, including schedule of planned interim analyzes

All the parameters collected will be presented in tables and diagrams containing descriptive statistics for each of the sub-populations (confirmation or not of GCA), as well as for the entire population analyzed, according to the following methods:

- for the quantitative variables: the number of missing values and non-missing values, the mean, the standard deviation, the 95% confidence interval, the median, the 1st quartile, the 3rd quartile, the minimum and the maximum,
- for qualitative variables: the number of missing values and non-missing values, frequencies, percentages and 95% confidence intervals, for each of the modalities of the variable.

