The analysis of the primary endpoint will consist of determining the positive predictive value of CDU and the algorithm will be considered valid in the absence of an alternative diagnosis within 2 years of follow-up in the group considered to have GCA. on a clinical-biological suspicion + "positive" echo-Doppler.

To establish a probability model of the clinical and paraclinical score calculation type, the variables significantly associated with the diagnosis will be determined by logistic regression. A number of points will be assigned to each variable based on the strength of its association with the diagnosis. The area under the ROC curve will be used as an indicator of the discriminative power of the score.

Correlation analyzes will be carried out to study a possible link between the description of the halos and the persistence of a poorer clinical response and to evaluate the inter-operator reproducibility for the reading of the TAB slides and Doppler echo images.

The analysis of diagnostic costs, induced costs, avoided costs, and efficiency indicators will make it possible to determine the costs/results of the diagnostic algorithm.

7.2- Expected number of people to be included in the research, and expected number of people in each research location with its statistical justification

According to a retrospective study of 42 patients treated for suspected Horton's disease, 70% of them had their Horton's diagnosis confirmed. To include at least 100 patients with Horton's disease over the study period, it is therefore necessary to include at least 142 patients suspected of Horton's disease (100 confirmed Horton's/42 other diagnoses). To take into account the possible overestimation of confirmed cases of Horton's disease due to biases of the retrospective study, the objective is to include 168 patients suspected of Horton's disease.

The population over 50 represents just over one million inhabitants in Charente-Maritime, Deux-Sèvres and Vienne. Considering an incidence of 1.2/10,000 inhabitants, approximately 120 new cases of Horton are detected each year.

Department	Number of people over 50	Number of new cases of Horton per year	Number of new Horton cases over 24 months	Estimation of the number of suspected cases of Horton over 24 months
Charente Maritime	491 871	59	118	168
Vienna	284,078	34	68	97
Two Sevres	261 272	31	63	90
Total	1037221	124	249	355

Table 2: theoretical recruitment potential

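### Section 7.5 can count CDU-positive patients without 2-year verification as GCA, and the validity verdict carries no bound for unverified patients

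*Combined protocol and SAP*

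**What the plan says.** Section 7.1 makes the PPV of CDU the primary analysis and adds a zero-event success rule: "the algorithm will be considered valid in the absence of an alternative diagnosis within 2 years of follow-up" among patients held to have GCA on clinical and biological suspicion plus a positive CDU. Under section 4.2.2.2 a positive CDU confirms GCA and no temporal artery biopsy (TAB) follows, so the 2-year follow-up is what verifies the diagnosis in this group.

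Section 7.5 sets the missing-data rule. Its trigger is "if less than 5% of the patients in the study are lost to follow-up or died". Below that level, "the missing data will be replaced by deductive imputation when possible". The single example takes patients whose clinical signs, biology and "examinations in favor of a horton and a good evolution under corticosteroids will be classified as suffering from" Horton's disease. Above it, the text says only: "In the event of a higher rate of missing data, other methods of managing problematic data will be considered".

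The plan also has safeguards. Section 7.5 states: "Missing data will be described in terms of numbers and corresponding percentages for each criterion and at each visit". Section 7.1 promises, for qualitative variables, "the number of missing values and non-missing values, frequencies, percentages and 95% confidence intervals". Section 4.5.1 asks for every effort to regain contact with lost subjects. Section 7.7 analyses eligible and evaluable subjects but does not define evaluable. No section plans a PPV restricted to verified patients, a worst-case bound or any other sensitivity analysis of the PPV.

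**The concern.** For a CDU-positive patient who is lost or dies before 24 months, the reference result is missing. The example in section 7.5 fills it in one direction only, towards GCA. The examinations it relies on are not said to exclude the CDU, and the CDU is the one examination that every patient in this group had in favour of GCA. The test under evaluation can therefore help to supply its own reference result. Good evolution is judged on corticosteroids, which section 7.5 says suspected patients receive.

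The 5% trigger is counted over the whole study, so nothing limits how many of the losses are CDU-positive. Under a zero-event rule, one misdiagnosed patient among the unverified would have failed the algorithm. The plan can declare validity without saying how far that possibility reaches. At 5% or more no method is named, which leaves the choice open until the data are in.

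**Working it through.** **Plan's own figure.** Section 7.2 reports that "70% of them had their Horton's diagnosis confirmed" in a retrospective series. Hence 100 / 0.70 = 142.9, against the plan's 142, which reproduces to rounding. The plan then raises the target to 168 by judgement. It states no number of CDU-positive patients and no target PPV or precision.

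**Losses allowed by the trigger.** 8/168 = 4.76% is under 5% and 9/168 = 5.36% is not, so at most 8 patients.

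**Size of the CDU-positive group (assumption).** Section 2.1 gives CDU sensitivities of 69% and 96%.
- From 100 GCA: 100 × 0.69 = 69 and 100 × 0.96 = 96.
- From 70% of 168 = 117.6 GCA: × 0.69 = 81 and × 0.96 = 113.

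The second pair is generous, because 168 was chosen in case 70% is too high.

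All intervals below are exact (Clopper-Pearson) 95%, with no observed alternative diagnosis. With n of n confirmed, the lower limit is 0.025^(1/n).

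**1. Effect of imputation alone, all 8 losses CDU-positive and all imputed.** The PPV is 100% in every cell.

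| CDU-positive | Lower limit, imputed | Lower limit, verified only | Difference (points) |
|---|---|---|---|
| 69 | 69/69: 94.79% | 61/61: 94.13% | 0.66 |
| 81 | 81/81: 95.55% | 73/73: 95.07% | 0.48 |
| 96 | 96/96: 96.23% | 88/88: 95.89% | 0.34 |
| 113 | 113/113: 96.79% | 105/105: 96.55% | 0.24 |

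The verdict is the same in both columns.

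**2. Worst-case bound, losses in proportion.** The expected number of CDU-positive losses is 8 × n/168, rounded to the nearest whole patient. All are counted as alternative diagnoses.

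| CDU-positive | Expected losses | Used | Worst-case PPV (95% CI) |
|---|---|---|---|
| 69 | 3.3 | 3 | 66/69 = 95.7% (87.8-99.1) |
| 81 | 3.9 | 4 | 77/81 = 95.1% (87.8-98.6) |
| 96 | 4.6 | 5 | 91/96 = 94.8% (88.3-98.3) |
| 113 | 5.4 | 5 | 108/113 = 95.6% (90.0-98.5) |

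**3. Outer bound, all 8 losses CDU-positive and all misdiagnosed.** 61/69 = 88.4%, 73/81 = 90.1%, 88/96 = 91.7%, 105/113 = 92.9%.

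In cases 2 and 3 the zero-event rule fails, while the plan as written would report 100% and a valid algorithm.

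**The case against.** The strongest reply is that the imputation hardly matters. A lost patient with no recorded alternative diagnosis adds no event to the primary count whether imputed or not, and case 1 shows under one point on the lower limit. This stands. A reader might infer that section 7.5 manufactures the 100% PPV or the valid verdict, and the documents do not support that. The rule does not erase an alternative diagnosis already recorded, and the leverage of a single patient comes from the zero-event rule.

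A reader might also infer that a positive CDU alone settles the missing diagnosis. It does not. The example also requires clinical signs, biology and good evolution, and it is only an example, applied where possible. Some patients will have angio-CT, angio-MRI or PET-CT at inclusion (section 5.1), or PET-CT or CT after an axillary or carotid halo (section 4.2.2.2). CDU images are reviewed blind (section 4.3.2). Circularity is possible and partial.

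Nor does the plan conceal the missing data. Counts are required for each criterion, and the main criterion is defined only in CDU-positive patients, so a careful reader could derive the worst case by subtraction. What remains is that nothing requires this beside the PPV, and the counts neither change whom the rule treats as confirmed nor qualify the verdict.

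Finally, the branch below 5% may not be the one that operates. Deaths count towards the trigger, and section 7.5 expects general-population mortality at an age that section 2.1 puts mostly at 70 to 80. The documents give no rate. As arithmetic only, 2.5% a year over 2 years reaches 5%, and then no method is specified. This supports a rule that holds at any missing rate.

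**Conclusion.** The concern holds as a should-fix, with high confidence in the reading of the text. Section 7.5 allows unverified CDU-positive patients to enter the primary PPV as GCA, partly on the test being evaluated, under a study-wide threshold of up to 8 of 168 and with no method named above it. The numerical effect of imputing is small: 0.2 to 0.7 points on the lower limit with 8 missing, and no change of verdict. The larger defect is the missing bound. With losses in proportion, the reported 100% could stand beside a worst case of 94.8 to 95.7%.

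These figures rest on an assumed 69 to 113 CDU-positive patients, no observed event and the maximum loss below 5%, although the plan expects few losses. They are bounds. A reader might take them, or the 88 to 93% outer range, as the likely true PPV. The documents do not support that, because patients imputed under the example must have evolved well on corticosteroids.

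**What to change.** For the primary endpoint, at any missing rate, do not impute GCA.

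- Report the PPV with an exact 95% CI among CDU-positive patients who have a 24-month diagnosis or an earlier alternative diagnosis. Class the rest as unverified.
- Beside it, give a best-case bound (all unverified are GCA, close to the present imputed result) and a worst-case bound (none are).
- State the validity conclusion together with the number unverified and the worst-case bound.
- List the last completed visit of each unverified patient, so that those followed to M12 are distinguished from early losses.
- Report withdrawals of non-objection only as a separate count, since section 5.4 bars use of their data.
- Define evaluable in section 7.7 to match.

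The cost is a change of analysis wording, two extra table rows and a short listing, with no new visits or tests. The downside is a slightly wider interval and a less favourable bound beside the verdict.
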